### **7.1.2 Randomization and Stratification**

No patient will be randomized.

### **7.1.3 Populations for Analysis**

#### **Primary endpoint:**

1. Complete remission rate of BTK inhibitor refractory MCL patients with ixazomib and rituximab at 16 weeks of therapy.

#### **Secondary endpoints:**

1. ORR using Lugano Criterion at 16 weeks. ORR is the summation of partial remission + complete remission rates.
2. PFS and OS is defined as the time from commencement of treatment to the date of progression and death from any cause, respectively. Progression free survival time is the time interval from the start date of treatment to the date of progression or death due to any cause whichever happened first. Overall survival time is the time interval from the start date of treatment to death date. Patients will be censored at the last follow-up date if progression or death didn't occur.
3. Tolerability: completion at weeks 8, 16, 28, 42 and 56. Toxicity measured using CTCAE V4.0.

### **7.1.4 Procedures for Handling Missing, Unused, and Spurious Data**

There will be no missing, unused or spurious data.

### **7.1.5 Demographic and Baseline Characteristics**

Clinical and laboratory characteristics, age, sex, stage, MIPI scores etc., will be scored and presented in tabular or percentage form.

### 7.1.6 Efficacy Analysis

Overall response and complete response at each of the pre-specified time points will be described as percentage with exact ninety-five percent (95%) confidence interval based on binomial distribution. PFS and OS curves will be described using Kaplan-Meier methods. The curves will be presented with 95% confidence intervals. Patients who are still on follow-up without experiencing the relevant event by the closeout date will be censored. The maximum grade of each toxicity will be described in tabular form as count and percentages.

### 7.1.7 Pharmacokinetics/Pharmacodynamics/Biomarkers

Patient immunity and MCL profile: Alterations in patient immune parameters and MCL profile during various (screening, end of cycle 4, end of cycle 8, end of cycle 15, and end of study) time points during therapy will be assessed by 8 colored flow cytometry, evaluating populations of T cell, regulatory T cells, PD-1 and PDL1 expressions to generate hypothesis for future studies in combination with checkpoint inhibitors or Bispecific antibody therapies. Blood and bone marrow samples will be collected under protocol LAB11-0342 (*Collection and use of samples from patients with lymphoma, multiple myeloma, and other plasma cell dyscrasias for translational research*, PI: [name]) and transported to specified laboratory. Participants will sign a separate consent for their samples to be collected under LAB11-0342.

Minimal residual disease (MRD) measurement by Flow Cytometry: a four color assay as per institutional pathology flow cytometry analysis, CD3, CD4, CD5, CD8, CD10, CD19, CD20, CD22, CD34, CD38, CD43, CD45, CD56, CD200 and Lambda and Kappa. Blood and bone marrow samples will be collected under protocol LAB11-0342 (*Collection and use of samples from patients with lymphoma, multiple myeloma, and other plasma cell dyscrasias for translational research*, PI: [name]) and transported to specified laboratory. Participants will sign a separate consent for their samples to be collected under LAB11-0342.

### 7.1.8 Safety Analysis

Adverse event monitoring, vital signs, physical examination, 12-lead ECG, and laboratory assessments will be evaluated. Guidelines for the management for TLS are provided below in

Section 7.1.8.1. A safety analysis will be performed for all subjects participating in the study who took at least 1 dose of study drug.

For patient safety, the event of grade 3 or higher peripheral neuropathy toxicity within the first two cycles will be monitored. A rate of higher than 20% is considered excessive.

The prior probability of grade 3 or higher peripheral neuropathy toxicity is modelled by beta distribution (Beta (0.2, 0.8)). Denoting the probability of toxicity by  $p$  (TOX), the following decision criterion will be applied: We will stop the current dose level and consider treating patients at a lower dose level for Ixazomib if  $\text{Prob}\{p(\text{TOX}) > 20\% \mid \text{data}\} > 0.90$

Patients will be monitored in a cohort of 6 according to the following stopping boundaries for grade 3 or higher peripheral neuropathy toxicity.

Number of patients evaluated	Recommend stopping if $\geq$ toxicities observed
6	3-6
12	5-12
18	7-18
24	Always stop with this many patients

The operating characteristics are summarized in the following table (based on simulations from 10,000 trials).

True Toxicity Rate	Prob(stop the dose early)	Average number of patients treated
0.05	0.0023	23.96
0.10	0.0182	23.69
0.15	0.0616	23.00
0.20	0.1439	21.76

0.25	0.2677	19.97
0.30	0.4214	17.77
0.35	0.5831	15.39

**7.1.8.1 Recommendation for Management of Tumor Lysis Syndrome (TLS)**

Event	Occurrence	Action
Tumor Lysis Syndrome		
Blood chemistry changes or symptoms suggestive of TLS	Any	Withhold the next dose. If resolved within 24 to 48 hours of last dose, resume at the same dose.
		For any blood chemistry changes requiring more than 48 hours to resolve, resume at a reduced dose by one dose level.
		For any events of clinical TLS, resume at a reduced dose following resolution.

**7.1.9 Interim Analysis**

If early progression occurs in 2 or more of the first 5 patients, or 4 or more of the first 10 patients prior to the first restaging at week 16, the study will be closed for future enrollment. Using this rule, the probability of stopping the study early is 81.3% after 5 patients and 89.6% after 10 patients when the true rate of early progression is 50%. Early progression is defined as greater than 50% increase in the sum of bidirectional tumor measurement or new lesion prior to the first restaging at week 16.

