## **4. STUDY DESIGN**

### **4.1 Overview of Study Design**

Open label, single center, single –arm, phase II testing the combination of ixazomib and rituximab in the treatment of subjects with relapsed or refractory MCL. The study will enroll 24 patients. The treatment plan starts with oral ixazomib at the US approved dose of 4 mg. All subjects will have disease restaging at 8 weeks. Rituximab IV will be given once weekly for the first 4 weeks. Rituximab IV will restart at cycle 3, and continue monthly until cycle 12.

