## 5. STUDY POPULATION

### 5.1 Inclusion Criteria

Each patient must meet all of the following inclusion criteria to be enrolled in the study:

1. Male or female patients 18 years or older.
2. Patients must have histologically confirmed diagnosis of Mantle Cell Lymphoma.
3. Patients must have measurable disease, as defined by at least one of the following:
  - Lymph node or mass 2 cm or greater, splenomegaly > 13 cm
  - Bone marrow only disease as per morphology or flow cytometry
4. Patients must have relapsed and/or refractory disease to at least 2 lines of therapy including either an anthracycline- or bendamustine- based regimen and a BTK inhibitor.
5. Patients must have an Eastern Cooperative Oncology Group (ECOG) performance status and/or other performance status 0, 1, or 2.
6. Patients must have normal organ and marrow function as defined below:
  - a. Absolute neutrophil count (ANC)  $\geq 1,000/\text{mm}^3$
  - b. Platelets  $\geq 50,000/\text{mm}^3$
  - c. Total bilirubin  $< 1.5 \times$  institutional upper limit of normal (ULN). In patients with documented Gilbert's syndrome, total bilirubin  $\leq 2.5 \times$  ULN.
  - d. AST (SGOT)/ALT(SGPT)  $\leq 3 \times$  ULN
  - e. Creatinine clearance  $\geq 30$  mL/min (See Appendix 11.2)
7. Patients must be willing to give written consent before performance of any study related procedures not part of standard medical care, with the understanding that consent may be withdrawn by the patient at any time without prejudice to future medical care.
8. Female patients who:

- Are postmenopausal for at least 1 year before the screening visit, OR
  - Are surgically sterile, OR
  - If they are of childbearing potential, agree to practice 2 effective methods of contraception, at the same time, from the time of signing the informed consent form through 90 days after the last dose of study drug OR,
  - Agree to practice true abstinence when this is in line with the preferred and usual lifestyle of the patient. (Periodic abstinence [e.g., calendar, ovulation, symptothermal, post-ovulation methods] and withdrawal are not acceptable methods of contraception.)
9. Male patients, even if surgically sterilized (i.e., status post-vasectomy), must agree to one of the following:
- Agree to practice effective barrier contraception during the entire study treatment period and through 90 days after the last dose of study drug OR,

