### **6.13 Termination of Treatment and/or Study Participation**

Patients will be informed that they have the right to withdraw from the study at any time for any reason, without prejudice to their medical care. The investigator also has the right to withdraw patients from the study for any of the following reasons:

- Adverse event
- Protocol violation
- Lost to follow-up
- Progressive disease
- Study terminated

At the time of withdrawal, all study procedures outlined for the End of Study visit should be completed. The primary reason for patient's withdrawal from the study should be recorded in the source documents and CRF.

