**11.3 SCHEDULE OF STUDY ASSESSMENTS**

Days (+/-3d)	Screening A	C1D1	C2D1	C3D1	C4D1	C5D1	C6D1	C7D1	C8D1	C9D1	C10D1	C11D1	C12D1	C13D1	C14D1	C15D1+	EOS (+/- 7 days)
Informed consent, review inclusion/exclusion, general medical history B	X																
Vital signs, weight and height	X	X	X	X	X	X	X	X	X	X	X	X	X	X	X	X	X
ECOG and B symptoms C	X	X	X	X	X	X	X	X	X	X	X	X	X	X	X	X	X
Physical Exam D	X	X	X	X	X	X	X	X	X	X	X	X	X	X	X	X	X
12 lead ECG and ECHO E	X																
PET/CT or CT scan F	X				X F				X F				X F			X F	X F
Bone marrow biopsy/aspirate G	X				X G				X G							X G	X
MRD assessment H	X				X H				X H							X H	X
Tumor biopsy	X																X
CBC, CMP, and Hepatitis Testing i,j	X	X	X	X	X	X	X	X	X	X	X	X	X	X	X	X	X J

Days (+/-3d)	Screening A	C1D1	C2D1	C3D1	C4D1	C5D1	C6D1	C7D1	C8D1	C9D1	C10D1	C11D1	C12D1	C13D1	C14D1	C15D1	
Quantitative Immunoglobulins	X																
Pregnancy Test	X																

Footnotes Table of Assessments

- A. Perform within 28 days prior to cycle 1 day 1. Assessments performed as standard of care may be used for screening. *BIOPSY TISSUES* obtained up to 8 weeks prior to start of C1D1 can be used as long as we have enough tissue for analysis.
- B. Written informed consent form(s) must be signed by the patient before any study specific procedures are performed.
- C. B symptoms: Unexplained weight loss>10% over previous 6 months, fever (>38C) and/or drenching night sweats.
- D. Complete physical exam at screening, including cardiovascular, respiratory, abdominal, lymph node, skin ENT, extremities and endocrinological examination. Targeted physical exams at subsequent visits, limited to systems of clinical relevance, (i.e., cardiovascular, respiratory, lymph nodes, liver, and spleen), and dose systems associated with clinical signs/symptoms.
- E. Single 12-lead ECG and Echo is required at screening. If clinically significant abnormality is noted by the attending physician, a referral to cardiology will be made.

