- F. CT scans must include neck, chest, abdomen, pelvis and include oral and IV contrast. PET/CT performed at screening, at the end of Cycle 4, at the end of cycle 8, at the end of Cycle 15, and at the End of Study visit if not performed within the last 2 months. After Cycle 15, CT scans will be performed every 4 months. If PET/CT is performed and includes a CT scan of sufficient diagnostic quality and provides bidimensional nodal and liver and spleen measurements, an additional dedicated CT is not required at the time point. MRI may be used in place of CT at investigator's discretion.
- G. Bone marrow biopsies/aspirates at specified time points are mandatory (Screening, at the end of cycle 4, at the end of cycle 8, at the end of Cycle 15, and at the End of Study visit ) unless shown to be clear on previous examination by multi flow cytometry minimum sensitivity 10-4. \* If patient has progression on the study, we do require Bone marrow biopsy/aspiration at progression. For example, if week 9 imaging study shows clear progression beyond a reasonable doubt, we would like to perform a bone marrow biopsy/aspiration for end of study.
- H. Minimal residual disease assessment by ASO PCR in mantle cell lymphoma patients and flow cytometry. Peripheral blood will be collected from all patients as well as bone marrow aspirates in those patients required to undergo bone marrow aspirate and biopsy will be collected at Screening, at the end of cycle 4, at the end of cycle 8, at the end of cycle 15, and at the End of Study visit. Collect 20 mL's of blood in EDTA and 5 mL of a bone marrow aspirate in EDTA. Transport within 4 hours at room temperature to appropriate laboratory.

- I. Blood chemistry: Sodium, potassium, chloride, BUN, creatinine, glucose, calcium, total protein, albumin, AST, ALT, alkaline phosphatase, total bilirubin, LDH, phosphate, uric acid, magnesium and bicarbonate.

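### The futility rule in 7.1.9 counts only progression before the week-16 restaging, which 11.3 makes the first scheduled on-treatment scan, while 4.1 places restaging at week 8

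*Combined protocol and SAP*

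**What the plan says.** Section 7.1.9 closes enrolment if early progression occurs in at least 2 of the first 5 or at least 4 of the first 10 patients "prior to the first restaging at week 16, the study will be closed for future enrollment". It then defines the event: "Early progression is defined as greater than 50% increase in the sum of bidirectional tumor measurement or new lesion", with the same before-week-16 limit repeated. It gives stopping probabilities of 81.3% after 5 and 89.6% after 10 patients at a true early-progression rate of 50%. Section 4.3 relies on this rule to end the study early.

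The documents give two times for the first restaging:

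- Section 4.1: "All subjects will have disease restaging at 8 weeks".
- Section 11.3, footnote F: "PET/CT performed at screening, at the end of Cycle 4, at the end of cycle 8". Cycles last 28 days (6.2, 6.4.1), so the first on-treatment scan falls at 4 × 28 = 112 days, or week 16. The schedule table has no earlier scan.

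Four other provisions affect what the rule can capture:

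- Section 6.13, on patients who leave the study: "At the time of withdrawal, all study procedures outlined for the End of Study visit should be completed". Footnote F asks for a scan "at the End of Study visit if not performed within the last 2 months".
- Section 5.1 accepts as measurable disease "Bone marrow only disease as per morphology or flow cytometry".
- The PFS definition (2.2, 7.1.3) counts death from any cause.
- The bone marrow row for progressive disease in the appended Lugano table (11.4) lists only new or recurrent findings.

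**The concern.** On the 11.3 schedule, the rule leaves out whatever is first found on the first scan planned to find it. Two other kinds of early failure also fall outside the definition: death without imaging, and worsening of existing marrow disease in a patient enrolled with marrow-only disease, who has no bidirectional measurement.

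The rule decides whether enrolment closes, and its boundaries are small, so counting or not counting a single patient can change the decision. If real failures go uncounted, the trial is less likely to stop than a reader would expect from 81.3% and 89.6%. If the team counts them at its discretion, the rule in use is no longer the one whose properties are stated.

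**Working it through.** **1. The plan's own figures.** Let p be the probability that a patient has a counted event, X the count in patients 1–5 and Y the count in patients 6–10.

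- First look: P(X ≥ 2) = 1 − (1 + 5)/32 = 0.8125 at p = 0.5.
- No stop at either look: P(X=0)·P(Y≤3) + P(X=1)·P(Y≤2) = (1/32)(26/32) + (5/32)(16/32) = 106/1024 = 0.1035.
- Stop by the second look: 1 − 0.1035 = 0.8965.

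Both stated figures reproduce, and 89.6% is the cumulative two-look figure. The p in these formulas is the rate of the *counted* event.

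**2. What is counted under each restaging time.**

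| Event before or at week 16 | If 11.3 is followed (first scan at week 16) | If a week-8 scan is done (4.1) |
|---|---|---|
| Progression seen on a week-8 scan | no such scan | counted |
| Progression seen on unscheduled or End of Study imaging before week 16 | counted | counted |
| New lesion seen before week 16, including in marrow-only patients | counted | counted |
| Progression first seen on the week-16 scan | not counted | not counted, but fewer such cases |
| Death without imaging | not counted | not counted |
| Worsening of existing marrow disease | not counted | not counted |

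The marrow row overlaps the week-16 row. Footnote G places the first scheduled on-treatment marrow sample at the end of Cycle 4, so apart from the sample required at progression, marrow worsening would mostly be found at week 16.

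**3. Reach of the End of Study scan.** Footnote A says of screening: "Perform within 28 days prior to cycle 1 day 1". Taking 2 months as about 61 days, a screening scan done 28 to 0 days before C1D1 still satisfies footnote F until day 33 to 61, about week 5 to 9. Up to then, a patient who withdraws need not have a new scan.

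**4. Effect on stopping at a true 50% early failure rate.** If a share c of true failures is counted, put p = 0.5c into step 1. The documents give no value for c, so these are assumptions.

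| c (assumed) | p | First look | Two looks |
|---|---|---|---|
| 100% | 0.50 | 81.3% | 89.6% |
| 90% | 0.45 | 74.4% | 83.4% |
| 75% | 0.375 | 61.9% | 70.4% |
| 50% | 0.25 | 36.7% | 41.2% |

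A second illustration, also assumed: one of the first 5 patients has marrow-only disease whose progression is not counted, and none of patients 6–10 does. The first look becomes P(Bin(4, 0.5) ≥ 2) = 68.8%, and two-look stopping 82.4%.

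**5. Stopping when every failure is counted.**

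| True rate | 10% | 15% | 20% | 25% | 30% | 50% |
|---|---|---|---|---|---|---|
| Two-look stopping | 8% | 18% | 29% | 41% | 54% | 90% |

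**6. Enrolment before the rule acts.** This was simulated (200,000 trials) at a true 50%, with evenly spaced entry, closure as soon as a boundary is crossed, and at most 24 patients. If every event is seen only at week 16, mean enrolment is about 12 at 2 per month, and about 8.6 at 1 per month (24 patients over the 2 years in 4.3). If events are counted as they occur under a constant hazard (assumption), it is about 8.5 and 7.0.

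**The case against.** The strongest reply is that no stated figure is wrong. Section 7.1.9 quotes its probabilities for early progression and defines that term in the same paragraph; it never claims to cover every failure. A rule confined to progression before the week-16 primary assessment is narrow but coherent, and the PFS definition belongs to a secondary endpoint and does not bind an interim rule. This stands as far as the arithmetic and the omission of death are concerned. It does not rescue the window, because on the 11.3 schedule the rule excludes the first scan planned to supply its events.

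Second, a week-8 scan under 4.1 would be counted and would shrink the main gap. That also stands, and it is why the conflict has to be settled first.

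Third, the appended Lugano table does not list worsening of existing marrow disease either. Section 7.1.9 is therefore no narrower than the appended criteria on this point, and the marrow gap is secondary.

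Some stronger readings are tempting, but the documents do not support them:

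- That the rule can never be triggered. Unscheduled and End of Study imaging before week 16 count, and 6.13 will produce some of it.
- That marrow-only patients can never have an event. A new lesion counts for them too.
- That the C4D1 scan mark or the week-9 scan in footnote G adds further conflicts. The mark carries footnote F, which places the scan at the end of the cycle, and week 9 is only an example.
- That the chance of stopping is known to fall to a given level. The share of failures missed is not in the documents and could be small.

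**Conclusion.** The concern holds as a fault in a stated rule. The event window in 7.1.9 ends just before the scan that 11.3 schedules first, and 4.1 gives a different restaging time, so the rule cannot be applied unambiguously as written. Confidence is high for the wording fault and for the conflict between sections. It is not high for the size of the effect.

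The 81.3% and 89.6% are correct for a 50% rate of the counted event. They describe a true 50% early failure rate only if every failure is counted. Two-look stopping of 83%, 70% or 41% shows the range for assumed shares of 90%, 75% or 50%. The omissions of death and marrow worsening should be resolved by an explicit statement; they are less important than the window.

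**What to change.** 1. Make 4.1, 7.1.9 and footnote F of 11.3 agree on when the first restaging takes place.
2. In 7.1.9, keep the present size and new-lesion criteria, and change the window to at or before the week-16 restaging, so that the week-16 scan counts.
3. State in 7.1.9 whether death from any cause counts and whether marrow worsening counts. If marrow worsening counts, define it for patients enrolled with marrow-only disease, because the appended table does not.
4. Report two-look stopping probabilities for the final event at 10%, 15%, 20%, 25%, 30% and 50% (the table in step 5 of the working), so that the sponsor can confirm the 2-of-5 and 4-of-10 boundaries or recalibrate them.

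Cost: if the conflict is settled at week 16, this is a change of wording that uses scans and marrow samples already scheduled. Settling it at week 8 would add a scan to 11.3. Fuller counting raises the chance of stopping at every true rate, including 29% at a true 20% and 54% at a true 30%, which is why item 4 is needed. Each look is complete only when its patients reach week 16 or have an event, although a boundary can be crossed sooner. If events surface only at week 16 and accrual is 2 per month, about 12 patients would be enrolled on average at a true 50% rate.

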#### Rituximab Administration

Pre-medication consisting of acetaminophen and diphenhydramine should be considered before each infusion of rituximab to attenuate potential infusion reactions. Since transient hypotension may occur during rituximab infusion, consideration should be given to withholding antihypertensive medications 12 hours prior to rituximab infusion.

Rituximab First Infusion\*: The Rituximab solution for infusion should be administered intravenously at an initial rate of 50 mg/hr. Rituximab should not be mixed or diluted with other drugs. If hypersensitivity or infusion related events do not occur, the infusion can be escalated to 50 mg/hr increments every 30 minutes, to a maximum of 400 mg/hr. If hypersensitivity or an

infusion- related event develops, the infusion should be temporarily slowed or interrupted. The infusion can continue at one-half the previous rate upon improvement of patient symptoms.

Subsequent Rituximab Infusions: Subsequent Rituximab infusions can be administered at an initial rate of 100 mg/hr, and increased by 100 mg/hr increments at 30 minute intervals, to a maximum of 400 mg/hr as tolerated.

\*Patients with peripheral blood involvement (leukemic presentation) as defined for this purpose as  $> 20,000$  lymphocytes per  $\text{mm}^3$  as determined by flow cytometry studies, rituximab will NOT be initiated on Day 1. In this case, ixazomib will be started alone. Rituximab may be initiated on the next cycle if the lymphocyte count drops to  $< 20,000/\text{mm}^3$  in peripheral blood. For such patients, or for those with high tumor burden, despite lymphocyte count  $< 20,000$  cells/ $\text{mm}^3$  (as determined by the principal investigator), infusion of rituximab may be abbreviated as outlined below. If the patient progresses despite one cycle of ixazomib, the patient will be taken off protocol.

Day 1 – Rituximab 50 mg/ $\text{m}^2$

Day 2 – If no cytokine release phenomenon is noted on Day 1 and the peripheral blood white cell counts have decreased to  $< 20,000$  cells/ $\text{mm}^3$  or  $< 25\%$  of base line WBC counts, then the dose of rituximab can be increased to 325 mg/ $\text{m}^2$  on Day 2 at PI discretion.

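### The futility count in Section 7.1.9 can miss early progression confined to blood, or to marrow already involved at baseline

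*Combined protocol and SAP*

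**What the plan says.** The rule is in Section 7.1.9: "If early progression occurs in 2 or more of the first 5 patients, or 4 or more of the first 10 patients", before the week-16 restaging, enrollment closes. The event is then limited to two findings: "Early progression is defined as greater than 50% increase in the sum of bidirectional tumor measurement or new lesion", again before week 16. Blood counts, marrow, spleen, removal for progression and death are not mentioned, and there is no reference to Lugano progressive disease. No other section widens the definition.

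Two groups of eligible patients matter here.

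- Section 5.1, item 3, accepts as measurable disease "Bone marrow only disease as per morphology or flow cytometry".
- Section 6.2 (Rituximab Administration) starts patients with more than 20,000 lymphocytes per mm³ on ixazomib alone, and adds: "If the patient progresses despite one cycle of ixazomib, the patient will be taken off protocol".

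On timing, Section 4.1 says "All subjects will have disease restaging at 8 weeks", while footnote F of Section 11.3 puts the first on-study scan at the end of cycle 4. Section 6.13 lists progressive disease as a ground for withdrawal and says "At the time of withdrawal, all study procedures outlined for the End of Study visit should be completed". Footnote F, however, waives the End of Study scan if one was done in the preceding 2 months. Footnote G requires a marrow examination at progression.

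**The concern.** The futility rule should stop accrual when the regimen is failing early. A rising lymphocyte count, or worsening of marrow disease present at baseline, is neither growth in a bidirectional measurement nor plainly a new lesion. Such a patient can leave treatment with progressive disease recorded as the reason and still be a non-event for futility.

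The thresholds are small enough for one patient to decide the outcome. Take one nodal progression and one blood-only progression among the first 5. As written, that is 1 of 5 and enrollment continues; with both counted it is 2 of 5 and enrollment closes. Three plus one among the first 10 works the same way. The cost is further enrollment of BTK-inhibitor-refractory patients after the protocol's own treatment decisions have shown the regimen failing.

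**Working it through.** **1. The plan's own figures.** Inputs from Section 7.1.9: stop at 2 or more of 5, or 4 or more of 10; event rate p = 0.50.

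- Stop after 5: P(X ≥ 2 | n = 5) = 1 − 1/32 − 5/32 = 0.8125.
- Stop by 10 (both looks): 1 − [P(X=0)·P(Y ≤ 3) + P(X=1)·P(Y ≤ 2)], where X is the count in the first 5 and Y the count in the next 5. This is 1 − [(1/32)(26/32) + (5/32)(16/32)] = 1 − 106/1024 = 0.8965.

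Both match the stated 81.3% and 89.6%.

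**2. Would a scan catch the leukemic patient anyway?** Section 6.2 removes this patient for progression after one cycle, at about day 28. That precedes both the week-8 restaging of Section 4.1 and the end-of-cycle-4 scan. Withdrawal triggers End of Study procedures, subject to the 2-month waiver. Footnote A sets the screening limit: "Perform within 28 days prior to cycle 1 day 1". The baseline scan is then at most 28 + 28 = 56 days old, inside 2 months (about 61 days), so no new scan is normally required. Visit windows of 3 and 7 days could take it to 56 + 3 + 7 = 66 days, in which case one would be. The marrow examination under footnote G is required, but worsening of known marrow disease does not meet the 7.1.9 definition.

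**3. The marrow-only patient.** Without a bidirectional measurement the first criterion cannot be met. The second is met only if a new lesion appears.

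**4. Size, as illustration.** The documents give no share f of early progressions that would go uncounted. Assume f = 10% to 25%, so the counted rate is p(1 − f), and apply the formulas in step 1.

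| True rate | f | Counted rate | Stop after 5 | Stop by 10 |
|---|---|---|---|---|
| 50% | 0 | 0.500 | 81.3% | 89.6% |
| 50% | 10% | 0.450 | 74.4% | 83.4% |
| 50% | 25% | 0.375 | 61.9% | 70.4% |
| 20% | 0 | 0.200 | 26.3% | 28.9% |
| 20% | 10% | 0.180 | 22.2% | 24.2% |
| 20% | 25% | 0.150 | 16.5% | 17.6% |

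At a 50% true rate the loss is 6.9 to 19.4 percentage points after 5 patients and 6.2 to 19.3 points by 10. The 20% rows show the cost of counting everything when early progression is less common.

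**The case against.** The best defense is that 7.1.9 chose an objective imaging event and calibrated the rule to it. The 50% scenario is stated for early progression as that paragraph defines it, so the probabilities are right. A rate of all progression is a comparison the plan never made. This stands: there is no wrong number here.

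A reader might infer that every leukemic or marrow progression goes uncounted. The documents do not support that. Section 6.2 says only that the patient progresses; it does not say the call rests on blood alone or is made without imaging. To be eligible, a leukemic patient also needs a node or mass, an enlarged spleen, or marrow-only disease, so some will have measurable nodes. Footnote G's example is progression seen on a week-9 scan, so unscheduled imaging is foreseen. New marrow involvement might be read as a new lesion.

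A reader might also infer that the Lugano table already makes these cases progressive disease. Table 3 in Section 11.4 does not clearly do so. Its marrow row lists only new or recurrent disease, and it has no lymphocyte-count criterion. Clear worsening of nonmeasured lesions appears only in the CT column.

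Two cautions bear on the remedy. Section 8.1.1 keeps patients with asymptomatic treatment-related lymphocytosis on treatment, so a rising count alone must not become an event. And the plan sets no threshold for leukemic progression, so a wider definition brings investigator judgement into a 2-of-5 rule. Both stand and shape the wording proposed below.

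**Conclusion.** The concern holds in a limited form. The two-part definition in 7.1.9 may leave out early progression confined to blood or to marrow already involved at baseline, in patients the protocol knowingly enrolls and may remove for that progression. No mandated scan at about week 4 reliably closes the gap. That one such patient can reverse the decision follows from the boundaries and needs no assumed rate.

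The size of the effect is unknown. The losses in the table rest on an assumed 10% to 25% share and should be read as illustration. The figures of 81.3% and 89.6% should not be reported as errors. The definition should be changed because the remedy is cheap and the present rule can yield a worse decision.

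**What to change.** Add to Section 7.1.9: *Early progression also includes Lugano 2014 progressive disease; any investigator-confirmed disease progression, including in blood or marrow, that takes a patient off protocol with progressive disease recorded as the primary reason; and death from lymphoma, in each case before the week-16 restaging. Asymptomatic treatment-related lymphocytosis (Section 8.1.1) does not count.* State that the 50% scenario refers to this wider event; 81.3% and 89.6% then stand. The study team should confirm that 50% is the rate at which they want that stopping probability for the wider event.

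No new test is needed. Under Section 6.13 the primary reason for "withdrawal from the study should be recorded in the source documents and CRF", and footnote G already requires marrow at progression.

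The price is more frequent closure when the regimen is acceptable. At a 20% true rate, with an assumed 10% to 25% now uncounted, stopping rises from between 22.2% and 16.5% to 26.3% after 5 patients, and from between 24.2% and 17.6% to 28.9% by 10. The added part also depends on investigator judgement, so a progression called in error would count; the confirmation requirement is there to limit that.
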